**Diagnostic Utility of MRI in Female Patients with Nipple Discharge:
A Prospective Trial**

NCT02818946

Document Date: June 20, 2016

Research Summary

1. Protocol Title:

Diagnostic Utility of MRI in Female Patients with Nipple Discharge: A Prospective Trial

2. Purpose of the Study:

The purpose of this prospective study is to determine the diagnostic value of MRI for the evaluation of patients with pathologic nipple discharge.

3. Background & Significance:

Nipple discharge, one of the most common reasons for referral to the breast imaging service, is often investigated by diagnostic mammography and sonography to evaluate for an underlying malignancy, the reported incidence of which ranges from 3 to 29% (1-7). If conventional imaging is negative, the patient may obtain further imaging with MRI, undergo ductography or ductoscopy, proceed to duct exploration and excision, or be observed (6, 8). Findings on breast MRI, in addition to the patient's symptomatology (frequency and volume of discharge) and risk of breast cancer, are used to inform the decision about whether to pursue surgery or watchful waiting (8).

Limited research suggests that MRI may have a role in the evaluation of patients with nipple discharge because of its ability to identify mammographically- and sonographically-occult disease and to guide surgical excision (2, 9-16). Previous research has drawn conclusions from small retrospective patient cohorts, and there is relatively wide variability in the reported diagnostic utility of MRI. Consequently, duct exploration and excision remains the gold standard diagnostic approach (6, 8, 17). However, duct excision is an invasive procedure that can be technically challenging, especially if the affected duct cannot be localized or if the intraductal lesion is located far posteriorly in the breast, and can result in complications, such as interruption of the neurovascular supply to the nipple-areolar complex, cosmetic deformity, and breastfeeding limitations (18).

Many women with nipple discharge and a negative conventional imaging workup undergo surgical excision, but few actually have underlying malignancy. MRI may be useful to improve patient selection in this setting; in particular, a high negative predictive value of MRI may obviate the need for invasive surgery in patients who do not require intervention for symptomatic relief (8, 9, 17). Our research group previously performed a retrospective study on this topic, which is currently under review for publication. The negative predictive value of MRI was found to be 100%, but this study was significantly limited by selection bias; that is, only certain patients, at the discretion of the breast surgeon, underwent MRI as part of their workup.

The purpose of the proposed prospective study is to determine the diagnostic value of MRI for the evaluation of patients with pathologic nipple discharge.

4. Design & Procedures:

Referral for breast MRI in patients with pathological nipple discharge has changed in recent years. Discussion with our breast surgeons indicate that referral for breast MRI has become routine for patients who present with pathological nipple discharge when in the past, referral was at the discretion of the breast surgeon. For our study, patients with pathologic nipple discharge (unilateral and bloody or unilateral and clear) will be identified in either surgery clinic with presenting symptoms or in breast imaging clinic in one of 2 ways: 1) on the requisition under the “indication for exam” as specified by the referring clinician, or 2) by the technologist who asks routine questions to the patient. These patients will undergo conventional imaging with mammography and breast sonography first. If conventional imaging is negative or non-diagnostic, the patient will be seen in surgical clinic (Clinic 2-2 next door to ours) and contrast-enhanced breast MRI will be ordered by the surgeon as part of clinical care. All patients will see a breast surgeon first before being approached for the study. Once a patient is identified as having a planned contrast MRI, they will be approached by a CRC or resident/fellow participating in the study. Our experience, based on a prior retrospective nipple discharge study, has shown that approximately 100 patients per year are encountered at our breast imaging clinic for evaluation of nipple discharge. We expect that approximately 75% will agree to participate in the study. This will yield a recruitment rate of 75 patients per year, hence the number specified in the study proposal. Bracco Diagnostics will provide seed funding for 2 years for an anticipated total of 150 patients.

We will only be obtaining data prospectively on patients who receive MRI's for clinical purposes (symptoms of pathological nipple discharge). When the clinical team notifies us that an MRI has been ordered for that purpose, we will consent the patients to document the results and follow-up. We will not be obtaining any MRI's on patient's for research purposes only. For that reason, we will be following clinical guidelines for obtaining creatinine, pregnancy tests, etc.

The following data will be collected and analyzed: patient age, characteristics of the discharge (laterality, spontaneous versus expressed, duration of time, color, presence of blood), imaging workup and findings, BI-RADS final assessment categories, pathology results from core biopsy and/or surgical excision, and clinical and radiologic follow-up data during the two years after presentation.

5. Selection of Subjects:

See above detailed paragraph

Inclusion criteria: female patients with unilateral and bloody nipple discharge OR unilateral and clear nipple discharge; clinical decision to have contrast enhanced MRI.

Exclusion criteria: male gender, non-English speakers, age < 21 years, lack of capacity to give legally effective consent

Note: It is highly unusual for lactating patients to present with pathologic discharge and therefore will likely not be identified for the study. There is a very small potential

risk associated with absorption of contrast medium into the breast milk, but there is insufficient evidence to exclude women who are currently lactating from the study.

Note: The costs of MRI will be covered by insurance. In the unlikely event that a patient's insurance denies coverage, the patient will be excluded from the study.

6. Subject Recruitment & Compensation:

The patient will be seen in surgical clinic (Clinic 2-2 next door to ours) and contrast-enhanced breast MRI will be ordered by the surgeon. Potential subjects will be contacted and introduced to the study by the designated Clinical Research Coordinator or resident/fellow participating in the project.

Recruitment will begin after approval of IRB and conclude after recruitment of approximately 150 subjects. No financial compensation to subjects will be provided.

7. Consent Process:

Please see Section 14 of the e-IRB submission form.

8. Subject's Capacity to Give Legally Effective Consent:

Subjects who do not have the capacity to give legally effective consent will not be included in this study.

9. Study Interventions:

Patients who choose to participate in our trial will have undergone mammography, breast sonography, and will be planning to have a contrast-enhanced breast MRI for evaluation of nipple discharge. The study interventions are collection of clinical data for research purposes.

10. Risk/Benefit Assessment:

Participation in this study poses minimal risk to patients. Risks to the subjects include loss of confidentiality.

Loss of confidentiality is unlikely because the study data will be stored in the PI's office and a shared drive.

There will not be any direct benefit to the subjects; however, this research may help improve the diagnostic workup of nipple discharge in future patients.

11. Costs to the Subject:

There is no cost to the subject as a result of this study. The costs of the MRI will be covered by insurance. No financial compensation will be provided.

12. Data Analysis & Statistical Considerations:

As discussed above, a high negative predictive value of MRI may obviate the need for invasive surgery in patients who do not require intervention for symptomatic relief. Based on a statistical consultation with [name] [name], we can achieve a negative predictive value of MRI of 95% with a margin of error of +/- 4.3%, if we recruit 100 subjects. Our goal is to recruit approximately 150 subjects, with the expectation that some patients will not receive adequate two-year follow-up.

The following data will be collected and analyzed: patient age, characteristics of the discharge (laterality, spontaneous versus expressed, duration of time, color, presence of blood), imaging workup and findings, BI-RADS final assessment categories, pathology results from core biopsy and/or surgical excision, and clinical and radiologic follow-up data during the two years after presentation.

The sensitivity, specificity, positive predictive value (PPV), and negative predictive value (NPV) for MRI for the detection of malignancy will be calculated using standard formulas. MRIs classified as BI-RADS categories 4 and 5 will be considered "positive," while those classified as BI-RADS categories 1, 2, and 3 will be considered "negative." For purposes of the analysis, MRI will be considered to be "false positive" imaging if the biopsied and/or excised lesion does not reveal malignancy. MRI will be considered "false negative" imaging if there is no suspicious finding on imaging (BI-RADS 1, 2, or 3) but subsequent pathology reveals malignancy.

13. Data & Safety Monitoring:

Consent forms will be stored in the PI's office. Patient names and medical record numbers will be recorded in a database on a shared drive only accessible by study researchers. Once data collection is completed, these identifiers will be discarded. Only basic demographic information (age) will be retained.

14. Privacy, Data Storage & Confidentiality:

Please see Section 12 of the e-IRB submission form.

References

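### The ±4.3% margin for NPV counts all 100 recruits in the denominator, but NPV is estimated only in evaluable MRI-negative women, so the stated precision may not be delivered

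*Combined protocol and SAP*

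**What the plan says.** Section 12 (Data Analysis & Statistical Considerations) gives the plan's only quantitative precision statement: "we can achieve a negative predictive value of MRI of 95% with a margin of error of +/- 4.3%, if we recruit 100 subjects". It then raises the target for one reason: "Our goal is to recruit approximately 150 subjects, with the expectation that some patients will not receive adequate two-year follow-up".

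The same section defines the test result. BI-RADS 4 and 5 count as positive, and "those classified as BI-RADS categories 1, 2, and 3 will be considered" negative. Sensitivity, specificity, PPV and NPV are to be calculated by the usual formulas.

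Section 4 (Design & Procedures) sets the time of enrolment: "Once a patient is identified as having a planned contrast MRI, they will be approached". Section 5 requires a clinical decision to have the MRI and sets no condition on its result. Section 4 also derives the total from accrual: about 100 patients a year, 75% agreeing, two years of funding. In its words, "This will yield a recruitment rate of 75 patients per year, hence the number specified in the study proposal".

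No section gives an expected MRI-positive rate, a follow-up loss rate, or a target number of MRI-negative women.

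**The concern.** NPV is true negatives divided by all test negatives with a known outcome. Women with BI-RADS 4 or 5 are not in that denominator, and neither are women whose outcome is never established. Because enrolment precedes the MRI result, some recruits can be MRI-positive. A margin worked out on all recruits is then too narrow.

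Section 12 itself expects positive MRIs, since it also promises sensitivity and PPV. If all 100 recruits were MRI-negative with an NPV of 95%, there would be 5 false negatives and no true positives. Sensitivity would be 0/5 and PPV undefined.

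NPV is the measure on which the plan rests its argument that some women might avoid surgery. A reader who relies on this sentence for how well NPV will be known may expect more precision than the study delivers.

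**Working it through.** **Inputs.** From Section 12: NPV 95%, margin ±4.3 points, 100 recruits, goal of about 150. The confidence level and interval method are not stated; 95% and the normal approximation (Wald) are inferred because they reproduce the figure. The MRI-positive rate and the follow-up loss rate are not in the documents, so all values used below are assumptions.

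**1. Reproduce the plan's figure.** Half-width = 1.96 × √(p(1 − p)/n). With p = 0.95 and n = 100: 1.96 × √(0.0475/100) = 4.27 points, which rounds to 4.3. Other choices at n = 100 do not give 4.3: Wilson 4.51, exact (Clopper–Pearson) 4.82, Wald with continuity correction 4.77, 90% Wald 3.58, 99% Wald 5.61.

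**2. Number needed in the NPV denominator.** n = 97 gives 4.34, which still rounds to 4.3. n = 96 gives 4.36, which does not. A strict 4.3 needs 1.96² × 0.0475 / 0.043² = 98.7, so 99 women. The rounded threshold of 97 is used below because it is the more lenient.

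**3. If 100 women are evaluable but some are MRI-positive.**

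| Assumed MRI-positive | n in NPV | Half-width (points) |
|---|---|---|
| 10% | 90 | 4.50 |
| 20% | 80 | 4.78 |
| 30% | 70 | 5.11 |
| 40% | 60 | 5.51 |
| 50% | 50 | 6.04 |

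This is also the position if the extra 50 recruits are all lost to follow-up, since 150 − 50 = 100. Four positives among those 100 are then enough to miss the figure (n = 96).

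**4. If 150 are recruited.** n = 150 × (1 − positive) × (1 − lost).

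| Positive | Lost | n in NPV | Half-width (points) | 4.3 met? |
|---|---|---|---|---|
| 10% | 20% | 108 | 4.11 | yes |
| 20% | 10% | 108 | 4.11 | yes |
| 20% | 20% | 96 | 4.36 | just missed |
| 30% | 10% | 94.5 | 4.39 | just missed |
| 30% | 20% | 84 | 4.66 | no |
| 40% | 20% | 72 | 5.03 | no |

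**5. Break-even at 150.** The MRI-negative fraction times the evaluable fraction must be at least 97/150 = 0.647 (99/150 = 0.66 for a strict 4.3). The tolerable loss is 1 − 97/(150 × (1 − positive)): 28.2% at 10% positive, 19.2% at 20% and 7.6% at 30%. With no loss at all, the figure holds up to 1 − 0.647 = 35.3% positive.

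**6. Shape of the interval (secondary).** Near 95% a symmetric margin understates the lower side. For 95/100 the exact 95% interval is 88.7% to 98.4%, so the lower arm is 95 − 88.7 = 6.3 points, not 4.3.

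**The case against.** The strongest reply is that the fault may lie in the wording and not in the calculation. The statistical consultation may have meant 100 analysable, or even 100 MRI-negative, women. Raising the goal to about 150 to cover incomplete follow-up makes sense only if 100 is an analysable number. The match to the formula shows that n is about 97 to 101; it does not show who those women are. This is fair, but it does not rescue the sentence. The text speaks of recruiting 100 subjects, no MRI-negative target appears anywhere, and neither account of the 150 (follow-up loss in Section 12, accrual and funding in Section 4) mentions MRI-positive women.

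The second reply is that the study will recruit about 150, so the test that matters is the 65% break-even, and that may be passed. This stands. A loss of precision cannot be shown from the documents, and the misses listed at 150 recruits are small: from under 0.1 to about 0.7 points. The 6.0 figure needs 50% MRI-positive among only 100 evaluable women, a combination for which the documents offer no support.

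The third reply is that the study is observational and descriptive, and the NPV eventually reported will carry its own denominator. This also stands, and it limits the consequence to the stated rationale. The choice of interval method is a separate, minor matter and adds little weight.

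**Conclusion.** The concern holds. The ±4.3 points follows only if essentially every one of the 100 recruits is MRI-negative and evaluable, which conflicts with the section's own definitions and with enrolment before the MRI result. That mismatch is certain, granted the inferred 95% Wald formula.

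Whether precision is actually lost is not determinable. With 150 recruits the figure is kept if about 65% or more are both MRI-negative and evaluable. Otherwise the margin widens, to about 5.0 points at an assumed 40% positive and 20% lost. How NPV will be calculated is unaffected. The sentence should be corrected because it is the plan's only precision statement and concerns its central measure.

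**What to change.** Restate the precision in Section 12 for evaluable MRI-negative women, give the two fractions as labelled assumptions with a range, and name the confidence level and interval method. For example:

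*NPV will be estimated in women with BI-RADS 1–3 and an established outcome. If 60–90% of about 150 recruits are MRI-negative and 80–90% are evaluable (assumptions), this gives about 72 to 121 women. An observed NPV of 95% would then have a Wilson 95% interval of about 87% to 98% (n = 72) or 90% to 98% (n = 121).*

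The range comes from 150 × 0.6 × 0.8 = 72 and 150 × 0.9 × 0.9 = 121.5. The percentages are placeholders. The group's retrospective cohort could inform them, with two cautions from the protocol: Section 3 says that "this study was significantly limited by selection bias", and Section 4 says that MRI referral has since become routine.

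The cost is one or two sentences, with no change to enrolment, data collection or analysis. The only downside is that the stated precision may look less favourable.

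### Section 12 promises a margin of +/- 4.3 points on an NPV of 95% from 100 recruits, but that margin needs about 100 MRI-negative women

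*Combined protocol and SAP*

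**What the plan says.** Section 12 (Data Analysis & Statistical Considerations) of the combined protocol and SAP gives one precision statement. It anticipates an NPV of 95% "with a margin of error of +/- 4.3%, if we recruit 100 subjects". It then sets a goal of about 150 and gives one reason for the surplus: "with the expectation that some patients will not receive adequate two-year follow-up".

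The same section classes BI-RADS 4 and 5 as positive, "while those classified as BI-RADS categories 1, 2, and 3 will be considered" negative. It adds that the "negative predictive value (NPV) for MRI for the detection of malignancy will be calculated using standard formulas". It names no confidence level, no interval method and no expected share of negative MRIs.

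Under Section 4 (Design & Procedures), women are approached once a contrast MRI is planned, so recruits will include both MRI results. Section 4 also gives a logistical basis for the sample size: "This will yield a recruitment rate of 75 patients per year, hence the number specified in the study proposal", with seed funding for two years.

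**The concern.** NPV is the proportion free of malignancy among women whose MRI is negative. Women with BI-RADS 4 or 5 contribute to PPV, sensitivity and specificity, but not to NPV. A margin for the NPV therefore depends on the number of MRI-negative women, and the plan attaches it to the number recruited.

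A second, smaller matter is the shape of the margin. Close to 95% the uncertainty about a proportion is not symmetric: there is more room below the estimate than above it.

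Both matter because Section 12 motivates the study with the argument that "a high negative predictive value of MRI may obviate the need for invasive surgery". The lower end of the interval is the informative end for that argument, and this is the only precision figure in the plan.

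**Working it through.** **Inputs.** From Section 12: NPV 95%, margin 4.3 points, 100 recruits, goal of about 150, negative = BI-RADS 1 to 3. Assumed, because the document gives no figure: MRI-negative share of 70% to 90%, and the follow-up shares in step 3.

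**1. Reproduce the stated figure.** Two-sided 95% Wald half-width = 1.96 × √(0.95 × 0.05 / n). At n = 100 this is 0.0427, or 4.3 points. A 90% level gives 3.6 and a 99% level gives 5.6, so 95% Wald is the natural reading. Only n of about 97 to 101 rounds to 4.3. The arithmetic is right, with about 100 women in the denominator.

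**2. Use the NPV denominator.** Same formula, per 100 evaluable recruits:

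| MRI-negative women | Wald half-width (points) | Evaluable recruits needed for 100 MRI-negative |
|---|---|---|
| 100 | 4.3 | 100 |
| 90 | 4.5 | 112 |
| 80 | 4.8 | 125 |
| 70 | 5.1 | 143 |

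**3. Check whether 150 recruits cover the gap.** Evaluable MRI-negative women = 150 × negative share × follow-up share. Reaching 100 requires the product of the two shares to be at least 100/150 = 67%.

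| MRI-negative share | All followed | 90% followed | 80% followed | Two thirds followed |
|---|---|---|---|---|
| 90% | 135 | 121.5 | 108 | 90 |
| 80% | 120 | 108 | 96 | 80 |
| 70% | 105 | 94.5 | 84 | 70 |

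If the whole surplus were used up by follow-up loss, which is the only purpose Section 12 gives it, 150 × 2/3 = 100 women would remain and all of them would have to be MRI-negative.

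**4. Check the lower end.** A symmetric margin implies a lower limit of 95 − 4.3 = 90.7%. The 95% intervals for 95 of 100 are:

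| Method | Lower | Upper | Implied 90.7% minus lower (points) |
|---|---|---|---|
| Wald | 90.7% | 99.3% | 0 |
| Jeffreys | 89.4% | 98.1% | 1.3 |
| Wilson | 88.8% | 97.8% | 1.9 |
| Clopper-Pearson | 88.7% | 98.4% | 2.0 |

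The half-widths of the last three are 4.3, 4.5 and 4.8 points. The methods differ mainly in where the interval sits, and less in how wide it is.

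**The case against.** The strongest reply is that the goal is 150, not 100. With 80% of MRIs negative and 90% of women followed, 150 × 0.80 × 0.90 = 108 women enter the NPV, and the Wald half-width is 1.96 × √(0.0475/108) = 4.1 points, slightly better than stated. Nothing in the document shows that the 67% condition fails. This stands, and it limits the point. A reader might infer that the study will miss its stated precision; the document does not support that, because it gives neither share. But the reply does not make the sentence about 100 recruits correct, and the plan itself explains the surplus by follow-up loss alone.

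It can also be said that a margin of error is a half-width, that Wald is an ordinary planning approximation, and that the plan states no lower limit. This largely stands. A reader might take the plan to promise a floor of 90.7%, but that floor is only implied by a symmetric reading. The gap below it also depends on the method, and part of the Clopper-Pearson gap reflects that method's conservatism. For these reasons the lower-limit remark is secondary.

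Finally, no operative element hangs on the 4.3: there is no NPV threshold or decision rule, and Section 4 derives 150 from the recruitment rate and the funding period. This stands too. A reader might conclude that the sample size is invalid, but the figure does not determine it.

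**Conclusion.** The point holds as a correction to a planning statement. The +/- 4.3 points is right for about 100 MRI-negative women and wrong as attached to 100 recruits, unless every MRI is negative. On an assumed 70% to 90% negative share, the same formula gives 5.1 to 4.5 points per 100 evaluable recruits, which is 0.8 to 0.2 points wider. At 150 recruits a shortfall is possible but not shown. Separately, the symmetric form understates the downside at 95 of 100 by 1.3 to 2.0 points, according to method.

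The conclusion rests on three inferences: the 95% level and Wald method, taken from the match to 4.3; the assumed MRI-negative shares; and the reading that a woman needs pathology or adequate two-year follow-up to count, which Section 12 suggests but does not state as a rule. It does not rest on which interval will be used for reporting, since the plan names none, and a better interval can be computed later from the same counts. The change is worthwhile and cheap, but not essential to the conduct of the study.

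**What to change.** In Section 12:

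- Tie the precision to the expected number of MRI-negative (BI-RADS 1 to 3) women with a known outcome, meaning pathology or adequate two-year follow-up, and state that evaluability rule.
- Give the assumed MRI-negative share and follow-up share that lead from about 150 recruits to that number.
- Replace the +/- 4.3% with the 95% Clopper-Pearson interval for that number, and say that the same method will be used when the NPV is reported.

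Examples, all at an observed NPV of 95%:

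| Cancer-free / MRI-negative with known outcome | 95% Clopper-Pearson interval |
|---|---|
| 76/80 | 87.7% to 98.6% |
| 95/100 | 88.7% to 98.4% |
| 114/120 | 89.4% to 98.1% |

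The cost is two or three sentences. The stated precision may look slightly less favourable, an MRI-negative share has to be assumed openly, and Clopper-Pearson is somewhat conservative (mean coverage 97.3% at n = 100 for true NPVs of 93% to 97%). Enrolment, data collection and care are unaffected.

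### Does judging a false positive by the sampled lesion, but a false negative by any later malignancy, leave the accuracy measures undefined?

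*Combined protocol and SAP*

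**What the plan says.** Section 12 sets three rules close together.

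- Test result, by examination: "MRIs classified as BI-RADS categories 4 and 5 will be considered" positive, and categories 1, 2 and 3 negative.
- False positive, by sampled lesion: "imaging if the biopsied and/or excised lesion does not reveal malignancy".
- False negative, by later pathology: "imaging if there is no suspicious finding on imaging (BI-RADS 1, 2, or 3) but subsequent pathology reveals malignancy".

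True positives and true negatives are not written out, and no sentence names the woman, the breast or the lesion as the unit. The data to be collected (Sections 4 and 12) include "pathology results from core biopsy and/or surgical excision, and clinical and radiologic follow-up data during the two years after presentation", but neither error rule mentions the two-year follow-up. Eligibility (Section 5) is for "female patients with unilateral and bloody nipple discharge OR unilateral and clear nipple discharge".

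The measure that motivates the study is NPV: "a high negative predictive value of MRI may obviate the need for invasive surgery". It is also the only one with a precision statement: "negative predictive value of MRI of 95% with a margin of error of +/- 4.3%, if we recruit 100 subjects".

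**The concern.** The two error rules work at different levels. An MRI-negative woman counts as having cancer if any later pathology is malignant, with no limit of site, side or time. An MRI-positive woman is judged by the lesion that was sampled. If that lesion is benign and a cancer lies elsewhere, or appears in follow-up, the literal rule makes her a false positive. She then sits among the women without cancer and drops out of the sensitivity denominator. The reference standard would depend on the test result, which is a recognised fault in diagnostic accuracy studies.

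The second worry is side. Discharge is unilateral, and the decision at stake is surgery on that breast. No rule says how a cancer in the other breast counts. Cancers are expected to be few, so one reclassified woman could matter.

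**Working it through.** **1. The plan's own figure.** The Wald half-width for NPV 0.95 with n = 100, taking a 95% confidence level (not stated), is 1.96 × √(0.95 × 0.05 / 100) = 0.0427. This reproduces the stated 4.3 points.

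**2. What the wording already settles.** BI-RADS is applied to MRIs, the labels false positive and false negative are attached to the MRI, and the study is sized in subjects. One examination per woman is the natural reading. The false-positive rule covers tissue from biopsy, excision or both, so a benign core biopsy followed by a malignant excision of the same lesion is not misclassified. What remains is a woman with a benign flagged lesion and a separate or later cancer.

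**3. Effect of such women.** The documents give no counts, so these are assumed: 100 women, 30 MRI-positive, 70 MRI-negative, 10 cancers, 1 missed by MRI, and k discordant women. Read literally, TP = 9 − k, FP = 21 + k, FN = 1 and TN = 69. With one reference for everyone, the k = 0 row applies whatever k is.

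| k | Sensitivity | Specificity | PPV | NPV |
|---|---|---|---|---|
| 0 | 9/10 = 90.0% | 69/90 = 76.7% | 9/30 = 30.0% | 69/70 = 98.6% |
| 1 | 8/9 = 88.9% | 69/91 = 75.8% | 8/30 = 26.7% | 69/70 = 98.6% |
| 2 | 7/8 = 87.5% | 69/92 = 75.0% | 7/30 = 23.3% | 69/70 = 98.6% |

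For k = 1 the shifts are 90.00 − 88.89 = 1.1 points (sensitivity), 76.67 − 75.82 = 0.8 (specificity) and 30.00 − 26.67 = 3.3 (PPV). The 95% Wilson interval for 9/10 is 59.6% to 98.2%.

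**4. Range of cancer counts.** Section 3 cites malignancy in nipple discharge generally, "the reported incidence of which ranges from 3 to 29" per cent, which is not a figure for this MRI-referred group. With C cancers per 100 women, 1 missed and k = 1, sensitivity is (C − 2)/(C − 1) read literally and (C − 1)/C with one reference:

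- C = 3: 50.0% against 66.7%
- C = 5: 75.0% against 80.0%
- C = 10: 88.9% against 90.0%
- C = 29: 96.4% against 96.6%

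If MRI misses no cancer (C = 10, k = 1), sensitivity is 100% either way. PPV moves from 10/30 = 33.3% to 9/30 = 30.0%, and specificity from 70/90 = 77.8% to 70/91 = 76.9%.

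**5. Why NPV stays put.** The discordant woman is MRI-positive, so the MRI-negative row (69 + 1) never changes. NPV would fall only if she were also entered as a false negative. Section 12 reserves that label for BI-RADS 1 to 3, and entering her in both rows would count her twice.

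**6. The other breast.** If both breasts are imaged (the documents do not say), each other-breast cancer in an MRI-negative woman lowers NPV by 1/100 = 1.0 point with 100 MRI-negative women, or 1/70 = 1.4 points with 70. Counting it as a miss errs against MRI.

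**7. What a replacement rule would do.** Take the discharging breast as the unit and any cancer in it as the reference. A woman whose flagged lesion was benign then becomes a true positive. With one such woman sensitivity is 9/10 = 90.0%, against 8/10 = 80.0% when the cancer must lie where MRI pointed. PPV rises to 30.0%, although 26.7% is the answer to whether the flagged lesion was cancer.

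**The case for a change.** The best case for a change is that a confidence interval covers sampling error, not a choice of reading made after the data are seen. Sensitivity for one discordant woman runs from 80.0% (site-matched) to 90.0% (per breast), and at 3 cancers per 100 the literal rule costs 16.7 points (66.7 − 50.0). The remedy looks cheap. Side is listed expressly for the discharge but not for MRI findings or pathology, and Section 13 discards identifiers once data collection ends, so a gap found late might not be closed.

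Part of this stands. The two error rules are not parallel, and the report should say which unit and reference were used. But the 3-cancer example needs one of only three cancers to be discordant and another to be missed, at the bottom of a range drawn from a different population. The 10-point spread lies between two alternatives to the present text, which itself gives 88.9%. Imaging findings and pathology results are both on the data list, and side and site would ordinarily come with them.

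The remedy is not free either. Section 12 expects some women to lack adequate two-year follow-up. A rule that treats absence of recorded malignancy as absence of disease would make MRI-negative women lost to follow-up true negatives and so raise NPV, the one measure the present wording leaves alone.

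**Conclusion.** No change to the plan is needed. The unnamed unit is missing detail that analysts would fill sensibly: one examination per woman, with every woman who proves to have cancer counted as having it. The literal misclassification is confined to MRI-positive women with a benign flagged lesion and a separate or later cancer. One such woman costs 1.1 points of sensitivity, 0.8 of specificity and 3.3 of PPV in the assumed base case, and with none the readings agree. NPV and its 4.3-point margin do not move.

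Woman, discharging breast and lesion are all defensible units, and moving between them trades one imperfection for another. The other-breast point depends on bilateral imaging, which the documents do not state. The sizes above rest on assumed counts. The conclusion would weaken if discordant women proved common relative to the cancers found, and nothing in the documents suggests that.
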